Scoliosis is broadly defined as deviation of the normal vertical alignment of the spinal column. Scoliosis is typically classified as congenital, neuromuscular, syndromic, or idiopathic and may be treated with observation, bracing, or surgical correction, depending on the severity and the clinical status of the patient.[1] Idiopathic scoliosis represents the most common pediatric subtype and has a prevalence of 0.5 – 5.2%, with an operative rate ranging from 3.9 – 9.8 operations per 100,000 members of the general population.[2-4] Post-operative pain following the surgical correction of pediatric scoliosis is inevitable and must be well managed to achieve the goals of patient comfort, early mobilization, and early discharge. As a result of the short- and long-term adverse effects of opioid use in the pediatric population, many practices are adopting multimodal pain management strategies to reduce the reliance on opioid analgesia.[5, 6]

Virtual reality (VR) has been extensively studied in regards to its ability to reduce peri-procedural pain and anxiety in a pediatric population.⁷ Non-pharmacological methods of distraction are a well-established method of pain control. Virtual reality, by providing a more interactive and immersive experience, has the potential to out-perform other distraction techniques. However, the specific impact of VR following scoliosis surgery has yet to be assessed.⁸ At Connecticut Children's, patients undergo multimodal pain management following scoliosis correction, including narcotics, muscle relaxants, anti-inflammatories, and gabapentin. Patients are also expected to participate with physical therapy daily. In the present study, we intend to investigate the effect of VR on subjective post-operative pain, total inpatient narcotic administration, and mobilization with physical therapy.

Research Question

Does implementation of VR reduce pain, reduce total narcotic administration, and increase mobilization with physical therapy in the immediate post-operative period following spinal deformity surgery in the pediatric population?

Primary and Secondary Aims

Primary Aim(s):

- To determine if virtual reality (VR) reduces the subjective perception of pain for pediatric patients in the acute post-operative period (until discharge) following spinal deformity surgery.

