All pediatric patients (ages 13-18) undergoing corrective scoliosis surgery at Connecticut Children's over a span of 12 months (03/01/24-03/01/25) will be approached by a study team member during the pre-operative stage with information and consent documentation about the study. If the patient acknowledges that they are interested and would like more information, then the study team member will complete the formal consent and HIPAA process with the patient and family. This will take place in a private setting, and the patient/family will be given ample time to read the consent and have any questions answered. As a part of the consent and HIPAA, patients will consent to the study procedures as well as the research study team accessing their medical record for data collection. Each patient's MRN will be entered into a secure password protected Excel enrollment log and be given a subject identification number for de-identification. During the consenting procedure, the patient will utilize the VR device for 5 minutes to screen for side effects and become accommodated to the device. In the event that the patient experiences side effects during this 5-minute period, they will be excluded from the study.

Retrospective chart review sample:

The retrospective chart review is intended to be used as a historical control to the prospective arm of the study. All patients in the retrospective time frame (02/01/19 - 02/01/24) will be identified using CPT codes (fusion codes: 22800, 22802, 22804 and instrumentation codes: 22842, 22843, 22844) as well as ICD-10 Code M41.* from Slicer Dicer. These patient's charts will be verified by a study team member to ensure they meet inclusion criteria, and then they will be entered into a using a secure password protected Excel enrollment log. Each patient's MRN will be recorded into the enrollment log and will be given a subject identification number for de-identification. Patients in this cohort will not be approached for consent as we will not collect identifiable information and only their deidentified medical record will be in review. It is also likely that some patients are no longer clinically active at Connecticut Children's, and therefore we would not be able to contact these patients for consent.

Study Retention/Withdrawal

Prospective Cohort:

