All patients will be admitted after surgery. It is anticipated that some subjects may opt to not continue with VR and withdraw from the study. Participants will be told that they may withdraw from the study at any time by reaching out to the PI, [name], or the study coordinator, [name]. Withdrawing from the study will not affect patient care. A patient may also decline participation for a VR session, but choose not to withdraw from the entire study. If a patient declines three consecutive VR sessions, then they will be withdrawn from the study. If a patient withdraws, any data already collected will be made de-identifiable and no further information will be collected. These patients will not be included in downstream analyses.

Retrospective Cohort:

These patients will not be approached for consent and therefore will not be able to withdraw from the study.

Study Procedures

Due to the limited number of corrective surgeries for scoliosis in a given year, a true randomized control trial cannot be performed. As such, a prospective cohort will be used – all patients undergoing surgery during the study period will be offered VR and will be assessed for pain, opioid usage, and mobilization following surgery. These outcome measures will be compared to data identified from a retrospective chart review of children receiving the same surgery but without an additional VR-intervention, thus serving as a historical control.

Prospective Arm:

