After consenting to the study, the following baseline assessments will be performed and collected from the patient during the pre-operative stage: pain level and vital signs (heart rate, blood pressure, O2 saturation). Starting on postoperative day 1, the prospective cohort will begin receiving VR. These sessions will occur twice daily, starting 30 minutes prior to the patient's scheduled PT appointments, and will be facilitated by a study team member. At the beginning of the session, a study team member will visit the patient's room and set up the virtual reality device. A study team member will try to stay with the patient for the duration of the VR session, but in the event that they are unavailable to do so, a member of the nursing team, physical therapy team, or a parent will remain with the participant. As such, there will always be an adult in close proximity to the participant while they use the VR device. The duration of the session will last approximately 20 minutes and will utilize a low physical load VR experience (underwater or space exploration). The goal of the VR experience is to immerse the patient in a setting that gives the experience of decreased weight bearing load to decrease their post-operative pain. The VR screen will display a simulated environment, such as an underwater exploration, in which the participant can interact with floating marine life and vegetation. If the patient experiences side effects or would like a break during the VR intervention, they can inform a study team member and remove the VR device. They are permitted to place the VR device back on and continue the session when they feel comfortable to do so. A session will be considered "failed" if more than 50% of the session is spent not using the VR device. During the post-operative stage, the above outcome measures will be reassessed daily immediately before and after VR and also following the PT session. After the patient is discharged, the total number of PT sessions and total administered opioids will be collected from the patient's medical charts. In addition to pain, opioid usage, and mobility data from the study, the following information will be collected from the patient charts and entered into REDCap: demographics, degree of scoliosis, surgical details, PT notes, pain medication regimens, associated pain scales, and relevant follow up notes. As the VR device will be shared between users, the device will be sanitized with UV LEDs by Cleanbox prior to the transfer between patients.

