
Retrospective Arm:

Eligible patients verified for the retrospective chart review will be entered into a secure Excel enrollment log and be deidentified by using a subject identification number. The MRN and subject ID will be entered into a linking file that will be password protected and only accessible to authorized study personnel. The following information will be collected from the patient charts: demographics, degree of scoliosis, surgical details, PT notes, pain medication regimens, associated pain scales, and relevant follow up notes. These data will be entered into REDCap in a de-identified manner and will only be accessible to authorized study team members.

Sample Size Justification

This study will utilize a convenience sample of patients presenting to Connecticut Children's for a scoliosis surgery within the study timeframe.

Feasibility, Accrual, and Duration of Accrual

Accrual will occur over a 12 month period (03/01/24 - 03/01/25). Approximately 60-80 patients undergo a surgical procedure for the correction of scoliosis annually at Connecticut Children's. We estimate ~40% will decline to participate, therefore we anticipate approximately 35-50 patients being included in the prospective arm of study. For the retrospective arm of the study, we approximate to include 350 patients for chart review.

Study Limitations

This study is limited in that we are only assessing the utility of VR to reduce pain in a specific patient population (pediatric patients undergoing surgical correction of scoliosis), at a specific time (the immediate post-operative period), at a single institution (Connecticut Children's), and within a relatively small sample size, which limits the generalizability of the study to apply to other patient populations. This study is also limited in that it utilizes a retrospective chart review as a historical control. By collecting data retrospectively, it is likely that the study team will encounter missing variables and will not be able to categorize pain as accurately as they would be able to in a prospective or true randomized control trial study designs.

Data Analysis

- Intention to treat analysis
- A biostatistician will assist in analysis
- Descriptive statistics (frequency, percentage, mean, standard deviation, median, and interquartile range) will be utilized to describe the two groups (VR and control)

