- Fisher's Exact test, independent t-tests, and Wilcoxon Rank Sum tests will be used for univariate analysis to compare demographics between the two groups (VR and control)
- Pain outcome:
 - Univariate analysis using independent t-tests or Wilcoxon rank sum tests will be used to compare the daily mean pain scales
- Opioid utilization outcome
 - Univariate analysis using independent t-tests or Wilcoxon rank sum tests will be used to compare the total inpatient dose of opioids administered

Administrative Organization/Roles and Responsibilities

- Principal Investigator - [name] - Connecticut Children's Division of Neurosurgery
- Co-Principal Investigator – [name] – UConn Department of Psychological Sciences
- Co-Principal Investigator – [name] – Connecticut Children's Division of Orthopedic Surgery
- Co-Principal Investigator – [name] MPH – Connecticut Children's Division of Pain and Palliative Medicine
- Student Coordinators and Responsibilities:
 - [name] – Study Coordinator
 - Study Design

- Data quality
- Data analysis
- Project management
- Manuscript drafting
- [name] – Medical student
 - Study design
 - Study Procedures
 - Data analysis
 - Manuscript drafting
- [name] – Medical Student
 - Study Design
 - Study procedures
 - Data analysis
 - Manuscript drafting

Use of Study Results

The data generated from this study will be used to re-evaluate the postoperative pain management pathway for pediatric patients in the post-operative period following spinal deformity surgery. These data will also be used for presentations / publications.

Study Budget

Item	Quantity	Per
VR Computer	1	\$3,100
VIVE Wireless Head Mounted Display	1	\$1,100
Cleanbox	1	\$2,000
Computer supplies (external hard drives, batteries, sanitizer wipes)	1	\$200
VR Software	1	\$500
TOTAL		\$6,900

References:

1. Janicki, J.A. and B. Alman, *Scoliosis: Review of diagnosis and treatment*. Paediatr Child Health, 2007. **12**(9): p. 771-6.

2. Al-Mohrej, O.A., S.S. Aldakhil, M.A. Al-Rabiah, and A.M. Al-Rabiah, *Surgical treatment of adolescent idiopathic scoliosis: Complications*. Ann Med Surg (Lond), 2020. **52**: p. 19-23.
3. Sung, S., et al., *Incidence and Surgery Rate of Idiopathic Scoliosis: A Nationwide Database Study*. Int J Environ Res Public Health, 2021. **18**(15).

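### Pain after surgery but before the first VR session has no reference role in the analysis, so an arm difference already present on day 0 would be reported as a VR effect

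*Combined protocol and SAP*

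**What the plan says.** - **Timing of VR** (Study Procedures, Prospective Arm): "Starting on postoperative day 1, the prospective cohort will begin receiving VR". The only earlier exposure is at consent (Sampling Method/Recruitment Process), where "the patient will utilize the VR device for 5 minutes to screen for side effects and become accommodated to the device".
- **Where patients are on the day of surgery** (Study Retention/Withdrawal, Prospective Cohort): "All patients will be admitted after surgery".
- **Chart data.** The Prospective Arm and Retrospective Arm sections give the same abstraction list: "demographics, degree of scoliosis, surgical details, PT notes, pain medication regimens, associated pain scales, and relevant follow up notes". Neither names the days, the frequency or the source of the pain scores.
- **Pre-operative baseline** (Prospective Arm): "pain level and vital signs (heart rate, blood pressure, O2 saturation". This is a study measurement described for the VR cohort only, and no analysis uses it.
- **Outcome window** (Primary Aim): pain "in the acute post-operative period (until discharge) following spinal deformity surgery". No start day is given.
- **Pain analysis** (Data Analysis): univariate t-tests or Wilcoxon rank sum tests "will be used to compare the daily mean pain scales". No adjustment, matching, negative control or change from a reference day is described.
- **Comparator.** Study Procedures calls it a historical control. Study Limitations accepts that this brings missing variables and less accurate pain data, but gives no analytic remedy.

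**The concern.** The arms differ in more than VR. Controls come from about five earlier years. The VR cohort is self-selected, with about 40% expected to decline, and patients with side effects in the VR screen are excluded, a filter the controls never passed. Era, charting practice and willingness to enrol could each shift pain scores, and the listed covariates may not capture them.

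Pain charted after the operation but before the first session reflects real surgical conditions and cannot have been changed by inpatient VR. A difference between arms at that point is evidence of something other than VR. The plan gives this comparison no role, so a gap present before treatment and carried through the stay would enter the primary result as benefit or harm from VR. The results are meant to inform the hospital's postoperative pain pathway, so a misattributed difference has practical consequences.

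**Working it through.** **Inputs from the protocol.** Feasibility section: 60-80 operations a year, about 40% declining, 35-50 in the VR arm and about 350 controls. Primary hypothesis: at least 1 point lower with VR.

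**Assumptions, since the protocol gives none.** Two-sided 5%; patient-level SD 1.5, 2.0 or 2.5; correlation (rho) between day-0 and later pain 0.3 to 0.7; normal approximation.

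**Step 1: the plan's own figures.** 60 x 0.60 = 36 and 80 x 0.60 = 48, consistent with 35-50. Five years x 60-80 = 300-400, midpoint 350. The arm sizes reproduce.

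**Step 2: the planned test when VR does nothing and a non-VR gap g exists.** SE = SD x sqrt(1/n + 1/350). P(significant) = Phi(g/SE - 1.96) + Phi(-g/SE - 1.96). For n = 35 and SD 2: SE = 0.355, 0.5/0.355 = 1.41, and P = 0.292.

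| VR n | SD | SE | P, gap 0.5 | P, gap 1.0 | Day-0 CI half-width (1.96 x SE) |
|---|---|---|---|---|---|
| 35 | 1.5 | 0.266 | 0.468 | 0.964 | 0.52 |
| 35 | 2.0 | 0.355 | 0.292 | 0.805 | 0.69 |
| 35 | 2.5 | 0.443 | 0.204 | 0.617 | 0.87 |
| 50 | 1.5 | 0.227 | 0.597 | 0.993 | 0.44 |
| 50 | 2.0 | 0.302 | 0.380 | 0.911 | 0.59 |
| 50 | 2.5 | 0.378 | 0.263 | 0.754 | 0.74 |

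The gap-1.0 column is also the power for a true 1-point VR effect. The planned test cannot tell the two apart.

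**Step 3: what a day-0 check can show.** If day-0 scores have the same SD, its power to detect a 0.5-point gap is the same 0.20-0.60. It is informative through its interval, not as a pass/fail test.

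**Step 4: change from day 0.** A gap that is constant from day 0 cancels, and the false-positive rate returns to 5%. With equal SDs, the SE is multiplied by sqrt(2(1 - rho)): 1.18, 1.10, 1.00 and 0.77 at rho 0.3, 0.4, 0.5 and 0.7. If day-0 SD were 2.5 against 2 later, at rho 0.4 the ratio is sqrt(2.5² + 2² - 2 x 0.4 x 2.5 x 2)/2 = sqrt(6.25)/2 = 1.25. With equal SDs, power for a true 1-point effect is 0.48-0.96 at rho 0.3, 0.62-0.99 at 0.5 and 0.83-1.00 at 0.7, against 0.62-0.99 for the planned test.

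**Step 5: what it cannot remove.** A 0.5-point gap that starts only on day 1 stays in the change estimate, which then rejects with probability 0.16-0.81 across the same range.

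**The case against.** The strongest objection is that the documents never mention day-of-surgery pain. A reader might infer that day-0 scores are already abstracted in both arms and simply ignored. The documents do not support that. They support only that patients are in hospital and that "associated pain scales, and relevant follow up notes" are on the list for both arms. Availability is a reasonable inference, to be confirmed by year and by scale. A daily comparison over a window with no start day may also already include day 0. That stands, but the plan would then treat day 0 as one more outcome day, not as a reference.

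A reader might also infer that a day-0 analysis would expose or remove any non-VR difference. It would not. Only gaps present on day 0 and constant afterwards cancel. Two asymmetries visible in the protocol arise once VR starts: VR patients are rated around VR and physical therapy sessions while controls have chart ratings only, and patients who withdraw are left out of the analysis. Using charted scores in both arms addresses the first; neither step addresses the second. Residual anaesthesia may blunt day-0 ratings, and VR patients had the brief screen and expected VR.

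Finally, a change score is not the only defensible analysis of non-equivalent groups. Adjustment for covariates, calendar time or the day-0 score are alternatives. This argues against making change from day 0 the main estimate, but not against prespecifying it as a sensitivity analysis.

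**Conclusion.** The point holds as a gap in the analysis plan with a cheap improvement. The pain comparison is unadjusted, the comparator is historical, and the pre-VR postoperative window has no reference role. A half-point non-VR gap already present on day 0 would be declared a significant VR effect with probability about 0.20-0.60, and a 1-point gap with probability about 0.62-0.99. These figures rest on the assumed SD and alpha and on the protocol's anticipated arm sizes. Nothing in the documents shows that such a gap exists.

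The documents do not support a claim that the primary estimate must be replaced, or that a clean day-0 result would validate the comparison. Day 0 offers a partial check of limited precision, and only if the scores prove to be available.

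**What to change.** First confirm that day-0 scores exist in both arms, for each calendar year, and which scale was used. Then add to the Data Analysis section, using routinely charted scores in both arms:

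1. **Negative control.** The VR-minus-control difference in mean pain from the end of surgery to the first VR session, with the same clock window in controls, reported with its 95% CI. Exclude this window from the VR effect estimate.
2. **Sensitivity estimate.** The arm difference from day 1 onward relative to day 0, as change from day 0, with a day-0-adjusted model alongside. Name one summary contrast in advance, so that an arm-by-day model does not produce several competing results.
3. **Interpretation.** If the effect does not persist in item 2, the conclusion should not attribute the difference to VR. State beforehand how persistence will be judged, from the estimate and its CI.
4. **Stated limits.** Only gaps constant from day 0 are removed; gaps starting on day 1 are not. Residual anaesthesia may blunt day-0 scores. A null day-0 result does not exclude a half-point gap.

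The cost is a check of data availability, a few lines of SAP text and one or two models, plus further abstraction if day-0 scores are not yet being collected. The SE of the change estimate may rise by about 10-20% if the day-0/later correlation is 0.3-0.4, and by more if day-0 scores are more variable.

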 - Hypothesis: The mean self-reported pain level using a 10-point numeric pain scale will be a minimum of 1 point lower in patients receiving VR compared to those in the control group.

Secondary Aims:

- To determine if VR reduces the total amount of inpatient narcotic use in the acute post-operative period (until discharge) following spinal deformity surgery.
 - Hypothesis: Patients receiving VR will have reduced total inpatient narcotic administration during their hospital stay compared to those in the control group.
- To determine if VR can facilitate earlier mobilization following spinal deformity surgery.

- Hypothesis: Patients receiving VR will participate in a fewer number of physical therapy (PT) sessions prior to receiving clearance for discharge by PT staff.

Outcome Definitions/Data Points Collected

Primary Outcome:

Pain will be measured through the 10-point numeric pain scale self-reported by the patient (patient's will be between 13-18 years of age).

Secondary Outcomes:

- Mobilization will be assessed by the number of PT sessions prior to receiving clearance for discharge by PT staff.
- Patient post-operative gross motor activity level will be measured via wearable Fitbit
- Opioid utilization will be assessed by calculating the total inpatient dose of opioids administered (as documented in the EMR) during the post-operative period.
- Side effects from virtual therapy, including headaches, vertigo, and nausea

Data collected:

- Patient demographics
 - Age, Sex, Race, Language, Ethnicity
- Patient Past Medical History
- Patient medication/drug history (prescription and recreational)
- Prior experience with VR
- Surgical details
 - # of spinal levels involved in fusion
 - Duration of surgery
 - Surgical blood loss
 - Need for transfusion
 - Complications
- Radiographic imaging
- 10-point numeric pain scale ratingsPhysical Therapy notes
 - Number of sessions prior to discharge clearance, timing of sessions, duration of each session, comments from each session,
- EPIC Medication History
- Length of stay
- Timing and duration of virtual reality sessions
- Side effects from virtual therapy sessions
 - Seizures
 - Loss of awareness
 - Headaches
 - Vertigo
 - Nausea
 - Eye strain / blurred or double vision
 - Eye or muscle twitching

- Involuntary movements
- Dizziness and lightheadedness
- Disorientation
- Impaired balance and hand-eye coordination
- Excessive sweating
- Increased salivation
- Drowsiness
- Fatigue
- Motion sickness

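### The primary daily mean pain has no stated source, start day or rule for combining days, so VR readings timed around sessions could be set against control chart scores of unstated timing

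*Combined protocol and SAP*

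**What the plan says.** The Primary Aim concerns "pediatric patients in the acute post-operative period (until discharge) following spinal deformity surgery". Its hypothesis is that mean self-reported pain "will be a minimum of 1 point lower in patients receiving VR compared to those in the control group". Outcome Definitions names the instrument, a 10-point numeric self-report scale, and no time point. The Pain outcome entry in Data Analysis reads: "Univariate analysis using independent t-tests or Wilcoxon rank sum tests will be used to compare the daily mean pain scales".

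VR starts on postoperative day 1, with two sessions a day ahead of PT. On timing, Study Procedures (Prospective Arm) says "the above outcome measures will be reassessed daily immediately before and after VR and also following the PT session". The general part of Study Procedures says of pain, opioid use and mobilization: "These outcome measures will be compared to data identified from a retrospective chart review of children receiving the same surgery".

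For controls, the Retrospective Arm section takes pain scales from the chart and gives no timing or frequency. The Prospective Arm section also abstracts chart pain scales for VR patients, in addition to the study's own pain data. Appendix A, the data collection tool, appears by title only in the text available.

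**The concern.** The primary outcome summary is incomplete. If the VR-arm mean is built from the study readings, part of it is measured just after the intervention, at a moment that does not exist for controls. A short distraction effect could then enter the mean and be reported as lower pain over the day.

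Post-PT readings are a different case. PT was routine care ("Patients are also expected to participate with physical therapy daily") and PT notes are collected for controls, so some control scores may also follow PT. These readings could push the difference the other way.

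Two VR-arm sources are collected and neither is designated, so the choice could be made after the data are seen. The same applies to the start day and to the way several days become one result.

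**Working it through.** **What is fixed and what is open**

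- Stated: the scale (Outcome Definitions), the daily unit (Data Analysis), and the end of the window at discharge (Primary Aim).
- Not stated: the source of the readings, which readings enter the mean, whether day 0 counts, and whether days are tested separately or combined per patient.
- Also unclear: the readings are described as daily while sessions are twice daily, so one or both sessions may be measured.

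**The plan's own figures.** No powered sample size is given. The accrual figures reproduce: 60 × 0.6 = 36 and 80 × 0.6 = 48, against the stated 35-50. For the retrospective arm, five years give 5 × 60 = 300 to 5 × 80 = 400, with midpoint 350 as stated.

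**Illustration of the session-timed reading.** The sizes below are assumed; the documents give none. Suppose VR has no lasting effect, a dip d is confined to the post-VR reading, and pain rises by r after PT. Let f be the share of control readings that follow PT. Assume also that pre-VR readings sit at the level of control readings not following PT. The three reading types carry weight 1/3 each, whether one or both sessions are measured.

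Shift in the VR mean = -d/3 + r × (1/3 - f)

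- d = 1.5, r = 0: -1.5/3 = -0.50. For d from 0 to 2 the range is 0 to -0.67.
- Dip needed to produce the whole hypothesised 1 point: 3 × 1 = 3 points.
- d = 1.5, r = 1: at f = 0, -0.50 + 0.33 = -0.17; at f = 1/6, -0.50 + 0.17 = -0.33; at f = 1/3, -0.50 + 0 = -0.50. Above f = 1/3 the PT term turns negative.

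**Effect of the choice of readings.** With d = 1.5 and no PT effect, the shift is 0 from pre-VR readings only, -0.50 from all three, -1.5/2 = -0.75 from the readings before and after VR, and -1.5 from post-VR readings only.

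**Chance of a significant result from a 0.50 shift alone.** Assume SD 1.5 to 2.5 and two-sided alpha 0.05, with n VR patients against 350 controls.

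SE = SD × √(1/350 + 1/n); probability = Φ(0.5/SE - 1.96) + Φ(-0.5/SE - 1.96)

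- n = 35, SD 2.5: SE = 0.443, probability 0.20.
- n = 50, SD 1.5: SE = 0.227, probability 0.60.

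**Separate daily tests.** For an assumed 3 to 5 days, each tested at 0.05, the chance of at least one false positive is 1 - 0.95³ = 0.14 to 1 - 0.95⁵ = 0.23 under independence. Days within a patient are correlated, so this is an upper illustration.

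**Chart scores in both arms.** If no study reading is charted, the 1.5-point dip contributes 0. Suppose instead that all six daily study readings are charted beside six routine ones (assumed). Simple pooling then gives -1.5 × 2/12 = -0.25, and leaving out the flagged study readings returns it to 0. With six 4-hour blocks, one routine reading in each and three study readings in each of two blocks, the affected blocks shift by -1.5/4 = -0.375 and the day by -0.375 × 2/6 = -0.125.

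**The case against.** The strongest reply is that the plan may already intend a chart-to-chart comparison. The chart items listed for the two arms are the same and include pain scales, and the wording in Data Analysis is close to that chart item. In the Prospective Arm section, the measures to be reassessed may be the baseline pain level and vital signs named earlier in the same paragraph. The readings around VR would then be a session-level assessment. Total opioid dose and number of PT sessions are collected after discharge and could hardly be reassessed around each session. This stands: the text supports either reading, but it does not choose.

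A reader might infer that the plan builds in a bias favouring VR. The documents do not support that. The session-timed source is not confirmed, post-PT readings could act in the opposite direction, and the timing of control scores is unknown. The sizes above are all assumed, and they leave out any time-of-day difference.

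Study Limitations does acknowledge missing variables and less accurate retrospective pain data. That concerns the quality of control scores, not VR-arm readings timed to the intervention, and it sets no alignment rule. Appendix A may hold a rule. Its content was not available, so the finding is limited to the text that could be read.

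**Conclusion.** The point holds as a gap in the definition of the primary outcome that carries a risk of bias. It does not establish a bias. Source, start day and combination across days are open; scale, daily unit and end of window are not. On one of two plausible readings, up to a third of the VR-arm mean would come from a moment with no control counterpart. Under the assumed 1.5-point dip and equal weights this is -0.50 before any PT effect, or -0.17 to -0.50 with an assumed 1-point PT rise and f from 0 to 1/3. Net direction and size remain unknown. This should be fixed, and the change is cheap; the grade rests on the undefined summary and not on these figures.

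**What to change.** In Data Analysis, state that:

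- The between-arm primary pain comparison uses chart-recorded numeric self-report scores in both arms, abstracted by one identical rule, with the same start day (saying whether day 0 counts) and the same postoperative days.
- These scores are reduced to one prespecified value per patient, for example the mean of that patient's daily means over a fixed set of days common to both arms. One primary test is made on that value. Say how patients discharged before the last of those days are handled.
- Charted readings in the VR arm that exist only because the study required them are flagged, and a sensitivity analysis is reported without them. Data collected already lists "Timing and duration of virtual reality sessions", which helps to identify them.
- The study readings before VR, after VR and after PT are reported only as a within-patient analysis of immediate change.

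Averaging within fixed time blocks is optional, where chart time stamps allow it. If Appendix A already holds such a rule, cite it in Data Analysis.

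The cost is plan wording, one abstraction rule and one flag, since chart pain scales are already collected in both arms. There are real downsides. About 350 control charts must be abstracted by the same rule. Chart scores may be noisier and less complete than timed readings. Their timing may also partly follow analgesic administration, which VR is expected to change: "Patients receiving VR will have reduced total inpatient narcotic administration during their hospital stay".
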